Exclusion Criteria	
 • Current or history of cardiovascular, pulmonary, neurological, endocrine, or renal disease that would preclude the involvement in the study. • TENS use in the last 5 years • Pacemaker • Uncontrolled blood pressure or diabetes • Neuropathic pain condition • Systemic autoimmune disorder (Lupus, PMR, RA, Psoriatic arthritis) • Spinal fusion – cervical or lumbar • Metal implants in the spine • Severe skin allergy to adhesive • Allergy to nickel • Pain less than 4 • Pregnancy • Epilepsy • Change in or new drug or treatment program within the last month or in the next 2months, i.e. must have a stable treatment plan • Unstable medical or psychiatric condition which in the opinion of the investigator could compromise the subject’s welfare or confound the study results
Planned Sample Size	Final sample size of 264 subjects divided into 88 subjects per group. We will recruit 316 subjects based on a 20% projected attrition.
Randomization	Patients will be randomly allocated on the second visit after a re-assessment of eligibility. We will use a permuted block schedule, stratified by site. The randomization schedule will be implemented using SAS v9.2 PROC PLAN, creating blocks of size 6 for each of the strata factors.
Study Device Dosage and Administration	
FDA Summary of Empi Select TENS Unit: TENS is a non-pharmacological agent which delivers electrical stimulation by a battery operated device via electrodes placed on the skin. TENS is considered to be a safe, inexpensive and non-invasive modality used to treat a variety of acute and chronic pain conditions.
 
510(k) Summary for 300 PV Complete Electrotherapy Systems 1. Manufacturer Empi [name]

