
Statistical Methods Aim #1- #4
	
Aim #1: The primary endpoint of Aim #1 is the change (visit 3- visit 2) in pain scores during movement. In order to evaluate the effectiveness of long-term use of TENS (Aim 1), the primary analysis will be the comparison of change in pain (with movement for those randomized to either active TENS, placebo TENS, or standard of care). The comparison of the change (visit 3 – visit 2) in pain for the three groups will be made using linear mixed model analysis for repeated measures with treatment group, time (visit2 and visit3), and treatment group*time interaction as the fixed effects. The test for the treatment group*time interaction effect corresponds to the test comparing mean change among the groups. Post-hoc pairwise comparison of mean change between groups will performed by test of mean contrasts estimated from the fitted linear mixed model with p-values adjusted using Bonferonni’s method to account for the number of tests performed (i.e. 3 tests for all pairwise comparisons). It is expected that the randomization will lessen the need for covariate-adjusted analyses. However, in the event that adjusted analyses are necessary, a secondary comparison of the change in endpoints for the three groups will be made by expanding the linear mixed model to include covariates. Potential confounders include age, race, ethnicity, educational attainment, marital status, TENS dose/intensity, change in opioid status, medication intake and use of rescue medications.
 
While every effort will be made to follow-up with patients, preliminary data suggests that approximately 10% of the patients will not return for follow-up. The ITT analysis will be performed using all available data for all randomized participants. In the presence of missing data, under the assumption of missing at random (MAR), linear mixed model analysis which can handle incompletely observed subjects and uses a likelihood estimation method will provide correct likelihoods and lead to valid estimates (ref1). However, since the data under analysis cannot distinguish if data is MAR or it is missing not at random (MNAR), sensitivity analysis will also be performed using pattern mixture models. Multiple imputations will be used for sensitivity analysis by imputing from a non-random pattern mixture model (ref2).
 
Furthermore, based on previous work, it is expected that approximately 5% of subjects randomized to active TENS may not receive a full dose of active TENS because they did not achieve the adequate intensity dose. In the primary ITT analysis, these patients will be included as randomized. However, as an additional analysis a modified ITT (mITT) analysis will be conducted. This analysis will utilize an ITT principle in terms of randomization but will be limited to those who achieved at least one adequate intensity dose.
 
(ref1) Molenberghs G. and Kenward MG (2007) Missing Data in Clinical Studies. John Wiley & Sons Ltd, West Sussex, England.

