
(ref2) Carpenter J and Kenward MG (2013) Multiple Imputation and its Application. John Wiley & Sons Ltd, West Sussex, England.

Aim #2: The primary endpoint of Aim #2 is the change (visit 3 – visit 1) in fear of movement scores. Secondary endpoints for this aim include changes in function, fatigue, resting pain, function, use of rescue analgesic medications, and quality of life. Additionally physical function measures will be determined using accelerometer data and data obtained during a course of specific functional tasks. Rescue analgesic medications will be recorded as number and dose of medications, indicators for increases or decreases in frequency or dose, and any utilization. Comparisons between the randomized groups for these outcomes will be performed as described in Aim 1. Additional analyses, using the change in fatigue, fear of movement, function, quality of life and resting pain measures as dependent variables in linear regression models, associations between these outcomes and changes in pain values will be investigated.

Aim #3: The primary endpoints of Aim #3 are the change (visit 3 – visit 2) in PPT and DNIC/CPM for those who complete one month of active TENS. After one month of active TENS, participants will be clinically evaluated and classified as responders or non-responders using recently published criteria for fibromyalgia subjects [7]. Comparisons of these physiologic parameters will be made in responders versus non-responders as described in Aim 1. Since responder status is not randomized, it is expected that that the linear mixed model will also include covariates such as change in opioid status, medication intake, and TENS use. Multiple variable logistic regression (with associated odds ratio estimates and ROC curves) will also be utilized to investigate factors related to being a responder or not.

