Aim #4: The primary endpoints of Aim #4 are the FIQR and SF-36 prior to randomization. PROMIS modules (also obtained prior to randomization) for depression, fatigue, pain behavior, pain interference, physical function, satisfaction with social roles, and satisfaction with discretionary social activities will be summarized and compared to validated FM instruments (FIQR and SF-36). Scores from each of the PROMIS modules will be compared to corresponding FIQR and SF-36 domains (see Table 1) by estimating Pearson correlation coefficients and testing for nonzero correlation. Multiple linear regression may also be used to investigate this relationship while controlling for potential confounding variables. Finally, FIQR, PROMIS, and SF-36 will be obtained at four different time points during this study (pre-treatment, randomized phase, and non-randomized active TENS). Summaries will include values at pre-treatment, changes from pre-treatment and percent changes. In addition to changes observed in the randomized phase, linear mixed models may also be utilized where treatment status (pre-treatment, randomized treatment, and non-randomized active TENS) is treated as a time-varying covariate to estimate the impact of changes in treatment status on these outcomes.

As an exploratory analysis, further investigation of changes in pain, responder

	status, and relationships between endpoints will be conducted for data collected during the non-randomized phase and will include those with an additional month of active TENS (originally randomized to active TENS) as well as those with a single month of active TENS (originally randomized to placebo TENS and no treatment control). Finally, exploratory examinations of the relationships between changes in pain, sensory, and quality of life measures may utilize multivariate methods (e.g. partial least squares and principal component analysis) and classification and regression trees.
Safety Measures	Physical Exam Vital Signs Clinical signs and symptoms Adverse Event analysis Increased pain with testing follow-up: Participants who experience an increase in testing will be contacted the day after testing about the status of the increase in pain (Added 12/2014) Safety analysis

Schedule of Visits and Evaluations.

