Aim #1	V3-V2	Pain NRS with movement (6MWT and FTSTS) for the treatment groups: active TENS, placebo TENS or standard care	
 • Linear mixed model analysis (LMM) for repeated measures with treatment group, time (V3-V2) and treatment group*time interaction as fixed effects. • Post-hoc pair wise comparison of mean change between all three treatment groups • p-values adjusted using Bonferroni method to account for the number of tests • Potential confounders include BMI, age, race, ethnicity, educational attainment, marital status, TENS dose/intensity, change in opioid status, medication intake, rescue medications; If there are differences between potential confounders, we will include covariates
Aim #1 Intention to Treat (ITT)	V3-V2	Pain NRS with movement (6MWT and FTSTS) for the treatment groups: active TENS, placebo TENS or standard care	
 • Intention to treat (ITT) analyses using all available data for all randomized participants will be used • If there are missing data, missing at random (MAR) LMM will be used. Sensitivity analysis will be performed using pattern mixture models since data cannot be determined if it is MAR or missing not at random (MNAR). Multiple imputation will be used for sensitivity analysis by imputing from a non-random pattern mixture model • Modified ITT (mITT) will be conducted to account for subjects who did not achieve adequate dose (based on previous work, 5% of subjects randomized to active TENS

			are expected to not achieve adequate dose). This will be limited to those who achieved at least one adequate intensity dose ^{73, 74} .
Aim #2	V3-V2	Primary: Fear of movement scores. Secondary: changes in function, fatigue, resting pain, use of rescue medications, accelerometry and quality of life questionnaires.	
 • Comparison between the randomized groups will be performed as described in Aim #1. • Additional analysis using the change in fatigue, fear of movement, function, resting pain measures and quality of life as dependent variable in linear regression models, associations between these outcomes and changes in pain values will be investigated.

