Aim #3	V3-V2	Change in PPT, CPM for those who complete one month of active TENS.	
 • Classification of participants who complete one month of active TENS as responders or non-responders using published criteria⁵⁰ • Linear regression models will assess for factors that predict responders and non-responders to treatment using data obtained prior to the intervention.
Aim #4	V2 V3 V4	Prior to randomization: FIQR and SF-36. PROMIS modules for comparison to FIQR and SF-36.	
 • Pearson correlation and testing for nonzero correlation between PROMIS modules (and corresponding domains of the FIQR and SF-36. • Multiple linear regression may also be used to investigate this relationship while controlling for potential confounding variables. • FIQR, PROMIS and SF-36 will be obtained at 3 time points and summarizes as values, changes from pre-treatment and percent changes, changes observed in the randomized phase. Time points are (1) V2: pre-treatment; (2) V3 randomized phase and (3) V4 non-randomized active TENS. • Linear models may be used where treatment status ((1) V2: pre-treatment; (2) V3: randomized phase and (3) V4: non-randomized active TENS) is treated as a time-varying covariate to estimate the impact of changes in treatment status.
Exploratory Analysis		Changes in pain Responder status Relationships between endpoints Relationships between changes in pain, sensory and quality of life measures	
 • Further investigation during non-randomized phase, two months of active TENS (initially randomized to active TENS and those with a single month of active TENS (initially randomized to placebo TENS or standard care) • Multivariate methods (e.g. partial least squares and principal component analysis and classification and regression trees.

--	--	--	--

Table 3: List of equipment, form per test and measure

Area	Form	Visit	Equipment: Clipboards, Pens, Computer/Form
	Screening Log	Pre Visit	Computer/Form
Surveys	Consent	1	Computer/Form
	Health History/Demographic	1	Computer/Form
	Diagnostic Confirmation	1	Computer/Form
	Eligibility Confirmation	1, 2	Computer/Form
	FIQR	1,2,3,4	Computer/Form
	MAF	2,3,4	Computer/Form
	TSK	2,3,4	Computer/Form
	Medication	1,2,3,4	Computer/Form
	SF-36	2,3,4	Computer/Form
	PROMIS	2,3,4	Computer/Form
	IPAQ	2	Computer/Form
	PSQLI	2	Computer/Form
	PSEQ	2	Computer/Form
	PCS	2	Computer/Form
	Blinding Question Researcher and Subject	3	Computer/Form

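### Aim #3 plans ROC curves for a responder model fitted in about 84–95 women with no internal validation, so the apparent discrimination will be optimistic by an amount that depends on an unstated number of predictors

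*Combined protocol and SAP*

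**What the plan says.** In the Study Synopsis (Statistical Methods, Aim #3), the primary endpoints of the aim are the visit 2 to visit 3 changes "in PPT and DNIC/CPM for those who complete one month of active TENS". Women are then classed as responders or non-responders. The mixed-model comparison of the two classes is followed by a second commitment: "Multiple variable logistic regression (with associated odds ratio estimates and ROC curves) will also be utilized to investigate factors" related to responder status.

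The Aim #3 row of the Data Analysis Plan table covers the same work. It gives "Classification of participants who complete one month of active TENS as responders or non-responders using published criteria", and then says that linear regression models will look for factors that predict the two classes from pre-intervention data. It does not mention logistic regression or ROC curves.

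On numbers, the Planned Sample Size row gives "Final sample size of 264 subjects divided into 88 subjects per group" and "We will recruit 316 subjects based on a 20% projected attrition". The Aim #1 methods text expects that "approximately 10% of the patients will not return for follow-up".

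The documents give no list or count of predictors for the responder model, no selection rule and no expected responder rate. They describe no split sample, cross-validation, bootstrap or shrinkage.

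**The concern.** A ROC curve is a statement about discrimination: how well the model separates responders from non-responders. When it is drawn on the women who supplied the coefficients, it counts chance patterns in those women as discrimination. The error always favours the model. It grows with the number of predictors, or with the number screened, and shrinks with the number of responders.

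Here the sample is one arm, the predictors are not named, and the stated purpose in the Data Analysis Plan is prediction from pre-treatment data. A reader of the trial report could take an area of 0.70 or more as evidence that women who benefit from TENS can be recognised in advance, when the same figure can arise with no predictive information at all.

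**Working it through.** **Analysis set.** The Aim #3 endpoints are changes from visit 2 to visit 3, so the completers of a month of active TENS are the women randomized to active TENS.

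- Planned arm: 264 / 3 = 88, which agrees with the plan.
- Recruitment: 264 × 1.20 = 316.8, which agrees with the plan's 316. Dividing instead, 264 / 0.80 = 330, does not.
- Recruited per arm: 316 / 3 = 105.3.
- Completers at 20% loss: 105.3 × 0.80 = 84. At 10% loss: 105.3 × 0.90 = 95.

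The working range is therefore 84 to 95, with the planned 88 inside it.

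**Responders.** The rate is not in the documents; 30–40% is assumed. This gives 84 × 0.30 = 25 to 95 × 0.40 = 38 responders. Per predictor, that is 2.5 to 3.8 with 10 predictors and about 1.3 to 1.9 with 20.

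**Null simulation.** Predictors are independent standard normal variables unrelated to response. A logistic model is fitted by maximum likelihood, and the ROC area is computed on the same women. The number of predictors is also an assumption, so a range is shown.

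| Predictors entered | Mean apparent area, n = 84–95, 30–40% responders | True area |
|---|---|---|
| 3 | about 0.60 | 0.50 |
| 5 | 0.63–0.65 | 0.50 |
| 10 | 0.69–0.71 | 0.50 |
| 20 | 0.77–0.81 | 0.50 |

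At n = 88 and 30% responders, the chance that the apparent area reaches 0.70 with no real predictor is 3% with 3 predictors, 10% with 5, 53% with 10 and 98% with 20. The same fitted models scored on new subjects average 0.50 in every setting.

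**Sensitivity, n = 88 and 30% responders.**

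- Predictors correlated at 0.3: 0.71 with 10 and 0.80 with 20, essentially unchanged.
- Univariate screening at p < 0.10 before the fit: 20 candidates leave about 2 in the model and give a mean area of 0.68; 30 candidates leave about 3 and give 0.72. A small final model chosen from the data is therefore not protected.

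**The two descriptions of the model.** The Synopsis says logistic regression with ROC curves. The Data Analysis Plan says linear regression. The outcome, responder or not, is binary in both places.

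**The case against.** The strongest reply is that the size of the problem rests on a number the plan never gives. That is right. With 3 to 5 predictors fixed in advance the null area is only about 0.60 to 0.65, which few readers would find impressive. A reader might infer from the long baseline battery, or from the list beginning "Potential confounders include BMI, age, race, ethnicity, educational attainment, marital status", that 20 or more variables will be entered. The documents do not support this: that list belongs to the Aim #1 row, as confounders of the between-group comparison, and collecting an instrument does not commit anyone to using it as a predictor.

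Three further readings are tempting and also go too far.

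- Taking 10% off 88 to reach 79 women removes attrition twice, because 88 is already described as final.
- The "classification and regression trees" in the exploratory paragraph are optional. They are aimed at relationships between changes in pain, sensory and quality-of-life measures, and are not presented as responder classifiers.
- One might expect the odds ratios to be exaggerated too, but the calculations here cover only the ROC area, so no figure can be given.

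It can also be said that responder status is studied again in the non-randomized phase, where up to 264 women would have had active TENS. At that size the null area falls to 0.61–0.63 with 10 predictors and 0.65–0.69 with 20 (20–50% responders). However, the plan labels that work exploratory, and Aim #3 itself is defined on visits 2 and 3.

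Finally, the analysis is investigative and supplementary. That limits the importance of the point but does not remove it: the logistic model and ROC curves are stated as things that will be done, and the Data Analysis Plan speaks of prediction.

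**Conclusion.** The point holds in a limited form. The plan commits to ROC curves from a responder model fitted in roughly 84 to 95 women and describes no internal validation, so the reported discrimination will be optimistic. If 30–40% respond and no predictor is real, the mean excess over 0.50 is about 0.10 with 3 predictors, 0.13–0.15 with 5, 0.19–0.21 with 10 and 0.27–0.31 with 20. The responder rate and predictor count are assumptions. That the bias is upward does not depend on them; its size does.

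The logistic and linear descriptions conflict on the page, and that conflict needs no assumption. Neither matter touches the primary endpoint or the PPT and CPM endpoints of Aim #3.

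**What to change.** In the Aim #3 text of both the Synopsis and the Data Analysis Plan:

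1. Name a short list of baseline predictors before the data are examined. If any selection will be made, state the rule.
2. Report the bootstrap optimism-corrected ROC area with a confidence interval, beside the apparent area. Refit the model in each resample, repeating any selection there. Take the area in that resample minus the area of the same refitted model in the full analysis set, and subtract the average of these differences from the apparent area.
3. Use one description of the model in both places. For a binary outcome with odds ratios and ROC curves, that is logistic regression.

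The cost is a few sentences, a little extra code and a less favourable ROC area. No new data are needed.

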Aim #3: To determine if active TENS alters pain processing in women with fibromyalgia and if improvement in clinical symptoms correlates with normalization of pain processing physiology. We will evaluate change in these physiologic parameters in responders versus non-responders as assessed clinically.

Aim #4: To determine if PROMIS is a useful instrument for assessing outcome for fibromyalgia by comparing to the revised version of the fibromyalgia impact questionnaire (FIQ-R).

Healthy Control Aims:

Aims:

Physically active women with fibromyalgia will have a similar phenotype (pain thresholds and conditioned pain modulation) and cytokine profile to physical active women without pain; conversely sedentary women with fibromyalgia will have a similar phenotype and cytokine release profile to sedentary women without pain.

Aim #5 will perform quantitative sensory testing to profile excitability and central inhibition in individuals with fibromyalgia and healthy controls; both sedentary and physically active individuals will be recruited in each cohort.

Aim #6 will examine for cytokine release profiles in immune cells (monocytes) from the sedentary and physically active individuals with and without fibromyalgia.

Study Synopsis

Protocol Title	Fibromyalgia Activity Study with TENS (Transcutaneous Electrical Nerve Stimulation)
Protocol Number	
Name of Sponsor	Funded by NIH NIAMS Performed at University of Iowa, Vanderbilt University
Investigational Product	TENS (Transcutaneous Electrical Nerve Stimulation) TENS is a non-pharmacological agent which delivers electrical stimulation by a battery operated device via electrodes placed on the skin. TENS is considered to be a safe, inexpensive and non-invasive modality used to treat a variety of acute and chronic pain conditions.
Phase of Development	Phase II Clinical Trial
Purpose of Study	The primary aim of the study is to test the effect of the long-term use of TENS on movement-related pain as measured by a numeric rating scale (NRS) during six minute walk test (6MWT) in women with fibromyalgia with random assignment to three treatments: standard care (No TENS), placebo TENS and active TENS.
Indication	Women with Fibromyalgia, ages 18-70
Number of Centers	The study will be conducted at 2 study sites: University of Iowa and the Vanderbilt University
Study Duration	5 years

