Criteria for Evaluation	
Primary Efficacy Endpoint:
 
 • Pain with movement (NRS) during 6MWT 
Secondary Efficacy Endpoints:
 
 • Health History/Demographics • Vital Signs • Confirmation of ACR 1990 Criteria for FM/Tender Point Exam • 2010 ACR Criteria • NRS Rest Pain, Rest Fatigue, Movement Pain, Movement Fatigue • BPI • PROMIS • FIQR • SF-36 • MAF • TSK • IPAQ • PSQI • PSEQ • PCS • Global Impression of Change • Accelerometry • 6MWT • STS • FR • PPT • CPM • TENS • Blinding
Statistical Methods	
 • Continuous variables will be summarized with descriptive statistics (n, mean, standard deviation, standard error, median, first and third quartiles, and minimum and maximum). • Categorical variables will be described with counts and percentages. The endpoints (VAS, BPI, PPT, CPM, and 6MWT, STS, FR and accelerometry measures) will be treated as continuous variables as well as scores from questionnaires (FIQR, SF-36, MAF, and TSK, PROMIS). • Changes from initial measurement to one month after randomization will be calculated for each of these endpoints. Changes in outcomes and percent changes in outcomes will be treated as continuous variables and will be summarized with descriptive statistics. Outcomes will be summarized by visit, as change from initial measurement, and percent

	
change from initial measurement. Continuous endpoints may also be categorized into discrete variables when appropriate. Shift tables may be utilized to investigate shifts in outcome categories from baseline to one month after randomization. SAS v9.2 or higher will be used for all analyses and a significance level of 0.05 will be used for all statistical tests. In the case that endpoints are found to be non-normal, appropriate transformations will be employed and non-parametric tests may be used

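### Aim #4 asks whether PROMIS is useful for assessing outcome, but its only committed comparison with FIQR/SF-36 is a pre-randomisation correlation tested against zero, with no comparison of change

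*Combined protocol and SAP*

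**What the plan says.** The Aims section states the purpose of Aim #4 as "To determine if PROMIS is a useful instrument for assessing outcome for fibromyalgia", by comparison with the FIQR.

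The Study Synopsis (Statistical Methods Aim #1-#4) then fixes the time point: "The primary endpoints of Aim #4 are the FIQR and SF-36 prior to randomization". The seven PROMIS modules in the comparison are also the pre-randomisation ones. Each module is to be compared with its corresponding FIQR and SF-36 domains "by estimating Pearson correlation coefficients and testing for nonzero correlation". The Aim #4 row of the Data Analysis Plan repeats this: "Pearson correlation and testing for nonzero correlation between PROMIS modules" and the matching domains. Neither place gives a minimum correlation, an agreement criterion or a criterion for responsiveness.

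The same synopsis paragraph goes further. Multiple regression may be used. FIQR, PROMIS and SF-36 are to be summarised over the course of the study as values, changes and percent changes. A mixed model with treatment status as a time-varying covariate may be fitted. No sentence says that change in PROMIS will be compared or correlated with change in FIQR or SF-36.

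The general statistical methods set the level: "a significance level of 0.05 will be used for all statistical tests".

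**The concern.** The question and the committed test do not match. An outcome instrument has to register change when patients change. A correlation between two questionnaires completed on one occasion before treatment shows that they rank patients similarly at that moment. It does not show that they move together afterwards.

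The null hypothesis is also weak. With a few hundred women, a test of zero correlation is passed by a relation far too loose for one instrument to stand in for another. A significant p-value would then be compatible with anything from a near-trivial association to a very close one. At stake is whether Aim #4 can answer its own question. A report that PROMIS correlates significantly with the FIQR could be read as support for its use as a trial outcome when the analysis had not examined that.

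**Working it through.** **Inputs**
- Final sample, from Planned Sample Size: "Final sample size of 264 subjects divided into 88 subjects per group".
- Recruited sample, same place: "We will recruit 316 subjects based on a 20% projected attrition".
- Level 0.05, from Statistical Methods. Sidedness is not stated; two-sided is assumed.
- Seven PROMIS modules, from the Aim #4 text.
- Assumed: complete pre-randomisation scores on between 264 and 316 women.

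**The plan's own figures.** 3 × 88 = 264, and 264 × 1.2 = 316.8, which agrees with the stated 316 to within rounding. No power, target correlation or threshold is stated for Aim #4, so there is no Aim #4 figure to reproduce.

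**Smallest correlation that passes.** Critical |r| = t / √(n − 2 + t²), with t the 97.5% point on n − 2 degrees of freedom.
- n = 264: t ≈ 1.969, so r = 1.969 / √(262 + 3.877) = 0.1208; r² = 0.0146.
- n = 316: t ≈ 1.968, so r = 1.968 / √(314 + 3.871) = 0.1104; r² = 0.0122.

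An r of exactly 0.12 gives p = 0.0515 at n = 264, a narrow miss, and p = 0.033 at n = 316. It passes from n = 268 upward.

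**Power against weak correlations, n = 264.** Power ≈ Φ(atanh(ρ) × √(n − 3) − 1.96).
- ρ = 0.2: Φ(0.2027 × 16.16 − 1.96) = 0.91.
- ρ = 0.3: Φ(0.3095 × 16.16 − 1.96) = 0.999.

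**Multiplicity.** None is stated for Aim #4. If Bonferroni were applied over seven tests (one per module, assumed), the critical r would rise only to 0.165 at n = 264 or 0.151 at n = 316.

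**What the interval offers instead.** Fisher's z: tanh(atanh(r) ± 1.96 / √(n − 3)). For an observed r of 0.7 at n = 264: 0.867 ± 0.121, giving 0.63 to 0.76. To show how an interval could discriminate, the table gives the observed r needed for the lower 95% limit to exceed some illustrative bars, none of which comes from the documents:

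| Bar for lower limit | n = 264 | n = 316 |
|---|---|---|
| 0.5 | 0.585 | 0.578 |
| 0.6 | 0.672 | 0.666 |
| 0.7 | 0.757 | 0.752 |
| Zero-null test, for comparison | 0.121 | 0.110 |

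**Are change data available?** Table 1 of the protocol schedules FIQR, PROMIS and SF-36 all at Visits 2, 3 and 4, so Visit 3 minus Visit 2 change exists for all three without new assessments.

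**Precision of an active-placebo contrast.** With 88 per arm, the standard error of each standardised difference is about √(2/88) = 0.151. If changes on the two instruments correlate at 0.6 (assumed), the standard error of the difference between them is 0.151 × √(2 × (1 − 0.6)) = 0.135, so the 95% interval is about ± 0.26.

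**The case against.** Four objections carry weight.

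First, a reader might infer that Aim #4 looks at one time point only. It does not. Changes in all three instruments are to be summarised and a longitudinal mixed model is allowed. Aim #2 also compares randomised groups on quality-of-life change, and Table 1 labels PROMIS a quality-of-life measure, so a between-group analysis of PROMIS change is probably planned there. This stands, and it narrows the gap. But these analyses take each instrument on its own. The exploratory section mentions relationships between endpoints and between changes in several kinds of measure, without naming an instrument pair or a criterion.

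Second, a reader might take the p-value to be the decision rule for usefulness. No sentence says so. The coefficients are to be estimated as well as tested, so a weak r would be visible. That also stands. What is missing is any statement of how r will be judged.

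Third, it is tempting to say that the test cannot fail, or always rejects. The documents give no PROMIS correlations. The synopsis refers to Table 1 for the module-domain pairs, but the Table 1 in the text is the schedule of measures. Without the pairs, one cannot confirm that each matches like with like. The calculation supports only this: a true correlation as low as 0.2 to 0.3 would very probably be declared nonzero.

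Fourth, any minimum r is a judgement, and an active-placebo contrast depends on TENS having an effect. Both are true, and both shape the fix.

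**Conclusion.** The point holds as a modest mismatch between question and analysis. The only committed comparison of PROMIS with FIQR/SF-36 is a pre-randomisation correlation tested against zero. It is passed at |r| of about 0.11 to 0.12, depending on how many women have scores, and it cannot show that PROMIS tracks change. No minimum correlation is set, and no comparison of change between instruments is planned.

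This rests on a two-sided 0.05 test and on complete pre-randomisation scores for 264 to 316 women. The size of the bar is not sensitive to these: even with an assumed seven-fold Bonferroni correction it stays below 0.17.

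The documents do not support the conclusion that Aim #4 ignores outcome data or that its result would carry no information, because r is reported and each instrument's change is described. The consequence is confined to Aim #4. The primary comparison of movement pain and the stated sample size are unaffected.

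**What to change.** In the Aim #4 text of the synopsis and in the Data Analysis Plan row:

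1. Base the conclusion on r with its 95% confidence interval for each module-domain pair, in place of the zero-null p-value, and list the pairs.
2. As the main addition, correlate the Visit 3 minus Visit 2 change in each PROMIS module with the change in the matching FIQR or SF-36 domain, with a 95% confidence interval.
3. As support, compare the standardised active-placebo difference in Visit 3 minus Visit 2 change on PROMIS with that on FIQR, using a paired bootstrap interval (resampling women, keeping both instruments together).
4. If the sponsor wants a minimum acceptable r, set it before the data are seen. Its value is the sponsor's judgement.

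The cost is revised wording and a little extra analysis, with no new visits or questionnaires. The limitation lies in item 3: at about 88 per arm the contrast is imprecise (roughly ± 0.26 under the assumption above), and if active and placebo TENS do not differ it says little about PROMIS. That is why the change-score correlation should carry the main weight.
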